9.5. VITAL SIGNS

Vital signs will be measured at the screening visit (Week -11), on baseline visit (Day -3 to -5), and at week 6, 12, 18, 24, and 26. Measurements of vital signs will include measurement of supine, sitting and standing blood pressure (BP) measurements, and heart rate. Only the BP measured in the sitting position will be used to determine eligibility. Orthostatic systolic and diastolic BP will be calculated as supine measurement - standing measurement.

For BP, pulse rate, and respiration rate, observed values and change from baseline will be summarized by treatment group and nominal visit using descriptive statistics (n, mean and median, standard deviation, Q1, and Q3, minimum and maximum). For BP, supine, sitting, standing, and orthostatic BP will be summarized. Subjects vital sign measurements, including scheduled and unscheduled visits, will be listed.

9.6. ELECTROCARDIOGRAM

A 12-lead electrocardiogram (ECG) will be conducted at the screening visit (Week - 11), on baseline visit (Day -3 to -5), at week 24, and at week 26. ECG parameters measured will be the RR interval, PR interval, QRS duration, and QT interval. Each ECG should also be assessed by the investigator for signs of ischemia, clinically significant hypertrophy, and clinically significant T-wave abnormalities or arrhythmia.

For each abnormal ECG result, the investigator shall ascertain if the observation represents a clinically significant change from the screening ECG for that individual subject (this determination, however, does not necessarily need to be made the first time an abnormal result is observed. The investigator may repeat the ECG to verify the results of the original result). If the ECG result is determined to be a clinically significant and abnormal change from baseline for that subject, it is considered an AE.

For the ECG parameters, observed values and change from baseline from scheduled visits will be summarized with descriptive statistics by treatment group and overall at each visit. The maximum change from baseline from scheduled visits will also be provided for ECG parameters.

For the ECG overall assessment, the number and percentage of subjects in each overall assessment category (normal, abnormal but not clinically significant, abnormal and clinically significant, missing) will be presented by treatment group and overall at each visit.

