3.2.2 Treatment Period

The treatment period will start at randomization (Visit V6) and end after 24 weeks. At the start of the treatment period, each subject will be provided investigational product, dosing instructions, and glycemic control diary in which to record symptoms related to any hyper- or hypoglycemic events as well as information related to the occurrence of such events. Subjects with uncontrolled hyperglycemia based on blood glucose levels may receive additional approved anti-diabetic rescue medications (see Prescription of Rescue Medication below). Bexagliflozin tablets will be orally administered in the morning with 250 mL of water prior to eating or drinking.

Each subject will participate in a telephone consultation at week 2 (Visit V7) for safety monitoring. Each subject will be instructed to return to the clinic at weeks 6, 12, 18, and 24 (Visits V8, V9, V10, V11, respectively) for efficacy assessment and safety monitoring, including review of adverse events and concomitant medication, evaluation of vital signs, electrocardiogram (ECG), and a physical examination, and for a blood draw and urine

collection for clinical laboratory. On the day of the clinic visit, a fasting time of approximately 10 hours must be confirmed prior to blood draw.

To minimize the effect of missing values on data analysis and study outcome interpretation, considerable effort will be made to prevent missing data, to train site staff to encourage study subject participation and to remain vigilant to signs of non-compliance, to remain in contact with study subjects who have withdrawn from the study to collect as nearly complete a data set as is feasible, and to determine all reasons for missing data.

Subjects will return to the clinic for a follow-up exit visit at week 26 (Visit V12) or two weeks after the last dose of investigational product if the subject terminates prior to week 24. Following the exit visit, subjects will be advised to see their primary physician and resume treatment to control their diabetes. The duration of participation for each subject can be up to 37 weeks depending on prior treatment status.

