3.4 Study Duration and Dates

Potential subjects will be screened within 3 weeks of the start of wash-out or run-in period. Eligible subjects who are taking a background OHA and sign the informed consent will start a 6-week wash-out period, followed by a 2-week single-blind placebo run-in period. Eligible subjects who are treatment naïve and sign the informed consent form will immediately start the 2-week single blind placebo run-in period. Subjects who remain eligible at the end of the run-in period will receive 24 weeks of treatment. All subjects who are randomized will be followed for 2 weeks after the last dose of investigational product. The overall study duration from screening to follow-up could be a maximum of 37 weeks. The duration of the overall study depends on the rate of subject accrual. For details of the schedule and nature of the investigations, see the Schedule of Events in Appendix 1

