1. GLOSSARY OF ABBREVIATIONS

Abbreviation	Description
ADA	American Diabetes Association
AE	Adverse Event
ANCOVA	Analysis of Covariance
ATC	Anatomical Therapeutic Chemical
BMI	Body Mass index
CEC	Cardiovascular Endpoint Committee
CI	Confidence Interval
CRF	Case Report Form
CTCAE	Common Terminology Criteria for Adverse Events
CV	Coefficient of Variation
dL	Deciliter
DSMB	Data and Safety Monitoring Board
ECG	Electrocardiogram
eGFR	Estimating Glomerular Filtration Rate
FPG	Fasting Plasma Glucose
GLP-1	Glucagon-like Peptide-1
GMI	Genital Mycotic Infection
GGT	Gamma Glutamyl Transferase
HbA1c	Hemoglobin A1c
HBsAg	Hepatitis B Surface Antigen
HCV	Hepatitis C Virus
Hct	Hematocrit
HDL-C	High Density Lipoprotein Cholesterol
Hgb	Hemoglobin
HIV	human immunodeficiency virus
ICH	International Conference on Harmonization

Abbreviation	Description
ITT	Intention to Treat
IVRS	Interactive Voice Randomization System
IWRS	Interactive Web Randomization System
LDL-C	Low Density Lipoprotein Cholesterol
LOCF	Last Observation Carried Forward
MACE	Major Adverse Cardiovascular Event
MCH	Mean Cell Hemoglobin
MCHC	Mean Cell Hematocrit
MCV	Mean Cell Volume
Max	Maximum
MedDRA	Medical Dictionary for Regulatory Activities
Mg	Milligram
MI	Myocardial Infarction
Min	Minimum
mL	Milliliter
MMRM	Mixed Model Repeated Measures
N/A	Not Applicable
NA	Not Applicable
Na	Sodium
NCI	National Cancer Institute
ОНА	Oral Hypoglycemic Agent
PP	Per Protocol
PR	Time from the beginning of the P wave to the beginning of the QRS complex in electrocardiogram
PT	Preferred Term
QRS	Graphical deflections corresponding to ventricular depolarization in a typical electrocardiogram
QTc	Time between the start of the Q wave and the end of the T wave in the ECG, corrected for heart rate
RBC	Red Blood Cell

Version 2.0

THR-1442-C-450

Abbreviation	Description
RR	Time between the start of one R wave and the start of the next R wave in the ECG
SAE	Serious Adverse Event
SAP	Statistical Analysis Plan
SBP	Systolic Blood Pressure
SD	Standard Deviation
SE	Standard Error
SGLT2	Sodium Glucose Linked Transporter 2
SI	Standard International System of Units
SMBG	Self-Monitored Blood Glucose
SOC	System Organ Class
SOP	Standard Operating Procedure
SS	Safety Set
T2DM	Type 2 Diabetes Mellitus
TC	Total Cholesterol
TEAE	Treatment Emergent Adverse Event
TG	Triglycerides
TLF	Table, Listing And Figure
UACR	Urine Albumin To Creatinine Ratio
UGE	Urine Glucose Excretion
UPT	Urine Pregnancy Test
UTI	Urinary Tract Infection
WBC	White Blood Cell

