3.4. BRIEF DESCRIPTION

THR-1442-C-450 is a multi-center, randomized, double-blind, placebo-controlled, parallel-group study. It is designed to compare the efficacy and safety of once daily oral administration of bexagliflozin tablets, 20 mg to bexagliflozin tablets, placebo, in treatment-naïve type 2 diabetic subjects or subjects previously treated with no more than one oral hypoglycemic agent (OHA).

All eligible subjects will start a 2 week placebo run-in period. Subjects who miss no more than one dose of the run-in medication, have fasting blood glucose values \geq 250 mg/dL on no more than two consecutive days, and who, at the baseline visit (Visit V5), have an HbA1c level between 7 and 10.5% and a fasting glucose level < 250 mg/dL will be eligible for randomization.

Approximately 210 subjects will be randomly assigned to receive oral bexagliflozin tablets, 20 mg or placebo, in a 2:1 ratio once daily for 24 weeks in an out-patient setting. Subjects with uncontrolled hyperglycemia based on blood glucose levels may receive additional approved anti-diabetic medications. Treatment group assignment at the start of the treatment period will be stratified by HbA1c level at the start of the run-in period (7.0 to 8.5% or 8.6 to 10.5%) and background anti-diabetes treatment status (treatment naïve or not).

Each subject will be contacted by telephone at week 2 (Visit V7) for safety monitoring and will be instructed to return to the clinic at weeks 6, 12, 18, and 24 (Visits V8, V9, V10, V11) for efficacy assessment and safety monitoring. Subjects will return to the clinic for a follow-up visit at week 26 or two weeks after the last dose of investigational product if the subject terminates prior to week 24 (Visit V12).

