6.4. ANALYSIS VISIT WINDOWS

Table 3 shows how data will be mapped to analysis visits prior to selection of records for analysis. All post-baseline visits, including unscheduled and early termination visits, will be mapped. After mapping the data to the analysis visits, the following rules will apply unless other handling is specified for a particular analysis.

- If multiple records are available within a single analysis visit window, the record closest to the planned assessment day will be selected for analysis.
- If 2 records are equidistant from the target day, then the later record will be selected.
- If a subject has no record in an analysis window, the subject will be considered missing at that visit.

1007728

Table 3 Analysis Visit Windows

Study Day Window	Scheduled day	Scheduled Visit/Week
Day 1 - 63	Day 42	Visit 8/Week 6
Day 64 - 105	Day 84	Visit 9/Week 12
Day 106 - 147	Day 126	Visit 10/Week 18
>= Day 148	Last Dose Date + 1	Visit 11/Week 24

^{*} Week 24 is the end of treatment visit for those subjects completing the study per protocol. For safety endpoint of lab, vital sign, and ECG, the first collection after assigned Week 24 and > 7 days from Week 24 visit will be considered as Week 26 visit.

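### SAP 9.6 specifies no heart-rate-corrected QT, and its secondary maximum-change output mixes the week 24 on-drug ECG with the week 26 off-drug ECG

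*SAP*

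**What the plan says.** On parameters, SAP 9.6 states: "ECG parameters measured will be the RR interval, PR interval, QRS duration, and QT interval". Protocol 6.8 gives the same four. The SAP glossary defines QTc ("Time between the start of the Q wave and the end of the T wave in the ECG, corrected for heart rate") and the protocol's abbreviation list has it too. The text of neither document uses it, gives a correction formula or plans a QTc summary, and the title of Table 14.3.6.2 names none.

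On timing, SAP 9.6 places ECGs at screening and then "on baseline visit (Day -3 to -5), at week 24, and at week 26". Protocol Appendix 1 and SAP Table 1 agree. Treatment ends at week 24. Protocol 3.4 says "All subjects who are randomized will be followed for 2 weeks after the last dose of investigational product", and SAP 3.4 describes a "follow-up visit at week 26 or two weeks after the last dose of investigational product" for those who stop early. The note under SAP Table 3 makes week 26 a separate analysis visit for ECG: "the first collection after assigned Week 24 and > 7 days from Week 24 visit will be considered as Week 26 visit".

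On outputs, SAP 9.6 summarises observed values and changes by arm at each visit, then adds: "The maximum change from baseline from scheduled visits will also be provided for ECG parameters". It does not restrict this to on-treatment readings, or say whether the maximum is signed or absolute. Protocol 6.8 also allows ECGs whenever clinically indicated. These are not scheduled visits, so they do not enter the maximum.

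Protocol 3.2.2 is looser than the schedule. For the clinic visits at weeks 6, 12, 18 and 24 it lists "evaluation of vital signs, electrocardiogram (ECG), and a physical examination" among the assessments.

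**The concern.** QT shortens as heart rate rises. A summary of raw QT therefore mixes repolarisation with rate, and a difference between arms in rate alone can mask or mimic a QT effect. Mean RR shown beside mean QT hints at this but does not correct it within subjects. A subject's maximum QT change cannot be corrected from a separately taken maximum RR change, because the two may come from different visits. If a correction is added after unblinding, its formula becomes a choice made with the data in view.

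A maximum change is normally read as the worst value on treatment. Here one of its two scheduled inputs was recorded about two weeks after dosing stopped, while an ECG taken on drug for a clinical reason is left out. If an effect fades after stopping, this output shrinks it. ECG results are a named safety endpoint (SAP 4.3), so the rule should measure what its label suggests.

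**Working it through.** The documents give no ECG figure, so there is nothing to reproduce. The check has one count from the schedule and two illustrations on assumed values.

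**Count.** Post-baseline ECGs in SAP 9.6, SAP Table 1 and Protocol Appendix 1: week 24 and week 26. For a subject still on treatment at week 24, the maximum is over one on-drug and one off-drug value. A subject who stops early may contribute only off-drug readings.

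**Heart rate and raw QT.** Assume Fridericia's relation and a constant corrected value of 400 ms. With RR = 60/HR in seconds, QT = 400 × (60/HR)^(1/3).

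- 70 bpm: 400 × (0.8571)^(1/3) = 380.0 ms
- 75 bpm: 400 × (0.8000)^(1/3) = 371.3 ms, a change of -8.6 ms from unrounded values
- 80 bpm: 400 × (0.7500)^(1/3) = 363.4 ms, a change of -16.5 ms from unrounded values

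At a constant 420 ms the changes are -9.1 and -17.4 ms. For a fall from 70 to 65 bpm, raw QT moves by +9.5 ms (400) or +10.0 ms (420).

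**Maximum of an on-drug and an off-drug change.** Assume that the changes at weeks 24 and 26 are bivariate normal with common SD (10 to 20 ms) and correlation ρ (0.3 to 0.7). The drug shifts the week 24 change by d and has no effect at week 26.

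- With d = 0, the mean maximum is SD × √((1-ρ)/π). SD 10, ρ 0.7: 10 × √(0.3/π) = 3.1 ms. SD 20, ρ 0.3: 20 × √(0.7/π) = 9.4 ms. Each arm shows this rise with no effect at all.
- With θ = SD × √(2(1-ρ)), the arm difference in the mean maximum is d·Φ(d/θ) + θ·(φ(d/θ) - φ(0)). The off-drug ECG supplies the maximum with probability 1 - Φ(d/θ).
- Example: SD 15, ρ 0.5, so θ = 15. For d = 5: 5 × 0.631 + 15 × (0.377 - 0.399) = 2.8 ms, off-drug share 0.37. For d = 10: 10 × 0.748 + 15 × (0.319 - 0.399) = 6.3 ms, off-drug share 0.25.

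A simulation of 1,000,000 pairs per setting, over SD 10, 15 and 20 and ρ 0.3, 0.5 and 0.7, gave:

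| True on-drug difference | Difference shown by the maximum | Share of maxima from week 26 (active arm) |
|---|---|---|
| 5 ms | 2.7 to 3.1 ms | 26% to 42% |
| 10 ms | 5.8 to 7.3 ms | 10% to 34% |

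Under these assumptions the maximum keeps about 54% to 62% of a 5 ms difference (2.7/5 to 3.1/5) and 58% to 73% of a 10 ms one (5.8/10 to 7.3/10). The week 24 row of the by-visit table estimates the whole difference.

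**The case against.** The strongest reply is that little information is lost. The by-visit table is the main output and already keeps weeks 24 and 26 apart. RR is summarised beside QT, pulse rate is summarised under SAP 9.5, and ECGs are listed by subject (Listing 16.2.9.2), so QTc could be computed later. The SAP sentence lists what is measured, QTc is derived, and the table shells might contain it. Clinically significant ECG changes become adverse events, and QT is not an event of special interest. Rate variation common to both randomised arms adds noise, not bias.

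Most of this stands, and it rules out four stronger readings that a reader might infer:

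- *The maximum is the headline ECG result.* It is a secondary addition to the by-visit summary.
- *The plan cannot tell a rate change from a repolarisation change.* A rate difference between arms would be visible in RR and pulse rate. What is missing is a prespecified within-subject correction.
- *Some sites will record four on-drug ECGs because of Protocol 3.2.2.* That passage is loose narrative. It also names a physical examination, which is not scheduled at weeks 6, 12 or 18 either. Protocol 6.8 sends sites to Appendix 1, and Sections 7.8 to 7.12 and SAP Table 1 agree with Appendix 1.
- *The maximum is off-drug half the time, so the comparison is biased.* One half holds only with no drug effect and exchangeable changes, and then both arms are affected alike.

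The reply does not remove the two gaps in the SAP text: no correction formula is fixed in advance, and the maximum as written includes an off-drug reading and excludes unscheduled on-drug ones.

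**Conclusion.** The point holds, at low severity. The SAP 9.6 text specifies no rate-corrected QT, although both inputs are collected. Its maximum-change rule mixes on-drug and off-drug ECGs, so it would dilute an effect that fades after dosing stops. The by-visit summaries, the hypothesis tests and the efficacy conclusions are untouched.

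The dilution figures rest on the assumed SD, correlation and complete disappearance of the effect by week 26. If the effect persisted, the dilution would be smaller. The heart-rate figures rest on Fridericia's relation and assumed rate changes; the documents state no heart-rate effect of the drug, so these figures do not measure bias in this trial. The finding on QTc concerns the SAP text only, since the shells were not available.

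**What to change.** In SAP 9.6:

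1. Derive QTcF = QT/RR^(1/3), with RR in seconds. Summarise it and its change from baseline by visit as the main QT measure, and keep raw QT as a supporting row. If the shells already carry a QTc row, state its formula in the text.
2. Define maximum change over on-treatment post-baseline ECGs, scheduled and unscheduled, or drop it. Restricted to scheduled visits it would only repeat the week 24 change. If it is kept, say whether it is signed or absolute, and set the on-treatment window so that it includes the week 24 ECG, whose target in SAP Table 3 is the day after the last dose. Week 26 stays in the by-visit table, labelled as off-drug.

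As a minor alignment, reconcile the list of assessments in Protocol 3.2.2 with Appendix 1.

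The cost is one derived variable, a few sentences in the SAP, one block of rows in the ECG table and one wording change in the protocol. It needs no additional ECG or data collection.

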9.7. PHYSICAL EXAMINATION

A complete physical examination will be conducted at the baseline visit (Day -3 to -5) and at week 26. The examination will include measurement of body weight, and a

1007728

general assessment of all body systems including the skin, head, eyes, ears, nose, throat, neck, heart, lungs, abdomen, lymph nodes, and extremities. An abbreviated physical examination will be conducted at screening visit 1 (Week -11) and at week 24, or clinically indicated. The examination will include body weight and height (height will be measured only at screening), and general assessment of the skin, heart, lungs and abdomen. Physical examination findings will be presented in a by-subject listing.

1007728

10. INTERIM ANALYSES

No interim analyses are planned.

11. DATA AND SAFETY MONITORING BOARD

An independent data and safety monitoring board (DSMB) will review descriptive summaries of accumulating safety, subject disposition and limited efficacy data every 6 months, or a frequency recommended by the DSMB.

A designated statistician who is not involved with the study operation will hold the treatment codes. The unblinded treatment information can be provided to the DSMB to facilitate the evaluation of any clinically important increase in the rate of a serious suspected adverse reaction or to the designated safety contact when the treatment information is required to determine if an expedited safety report must be submitted to regulatory agencies. The data outputs for this review will be created by an unblinded team. Personnel involved in the conduct of the study will not participate in the preparation of these outputs, receive the data, or participate in the unblinded portions of the DSMB meetings. More details will be provided for DSMB charter and DSMB SAP.

12. CHANGE FROM ANALYSIS PLANNED IN PROTOCOL

There is no change from analysis planned in protocol.

1007728

14. PROGRAMMING CONSIDERATIONS

The following conventions will hold for programming of outputs:

- SAS® Version 9.3 or higher will be used for programming and production
- The format of the table shells will be followed as closely as possible; however, in the course of programming and familiarization with the database, some changes may become necessary. All changes will be documented. Major changes will be documented through a formal amendment to this document.
- Patients in this study will be identified as "Subjects."
- Descriptive statistics will be displayed in the following order:

n Mean Standard deviation (SD) Q1 Median Q3 Minimum Maximum

- Decimal places: For summary statistics, the minimum and maximum will be reported with the same number of decimal places as the collected measure, the mean, LS mean (if applicable) and median will have 1 more decimal place than the measure collected, and the SD and confidence interval (CI) will have 2 more decimal places than the collected measure. For frequency distributions, percentages will be reported to 1 decimal place. For p-values, 4 decimal places will be reported or the SAS® p-value format of "< 0.0001" or "> 0.9999" will be reported.
- Unless otherwise noted, the denominator for percentages is the number of subjects in the applicable analysis population and treatment group.
- If the frequency for a particular table cell is zero, then "0", properly aligned, will be displayed (i.e. "0 (0.0%)" will not be displayed.)
- Non-numeric values: Where variables are recorded using < (e.g., "< 10" or " \leq 10") the numeric portion of the result divided by 2 will be used (e.g., < 10 and \leq 10 becomes 5) for summary; where variables are recorded using > (e.g., "> 10" or " \geq 10") the numeric portion of the result will be used (e.g. > 10 and \geq 10 become 10) for summary; the actual recorded results, (e.g. "< 10" or "> 10") will appear in listings.

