6.9.2.2 Urinalysis

Urine samples will be collected routinely at designated clinic visits from a clean catch sample. Urinalysis will be performed at the time points indicated in the schedule of events (Appendix 1 and Appendix 2). Investigator or staff should document if pre-menopausal female subjects are menstruating and note it in the source documents since hematuria is likely to be identified on dipstick urinalysis.

Urine samples will be transported to the central laboratory for urinalysis. Samples should be stored and shipped as detailed in the Laboratory Manual. Microscopy will be conducted if the subject has a positive result on the leukocyte esterase or nitrite dipstick tests to clarify the significance of the finding. Results of glucose measurement in the urinalysis must be suppressed from the laboratory reports so the sponsor, investigators, study coordinators,

pharmacists, study subjects, and the CEC members will remain blinded to the dosing assignment.

In addition, strips to assess leukocyte esterase and nitrite but not glucose will be provided for immediate assessment at the clinical sites. If more than traces of positive results are shown in the leukocyte esterase and /or nitrite testing, a urine culture should be performed in a designated laboratory regardless of patient reported signs or symptoms. Results of the urinalysis and possible urine culture will be documented in the CRFs.

Renal functional testing by UACR will be determined at time points specified in the schedule of events (Appendix 1 and Appendix 2).

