Urinalysis microscopy will be conducted if the subject has a positive result on the leukocyte esterase or nitrite dipstick tests to clarify the significance of the finding. Results of glucose measurement in the urinalysis must be suppressed from the laboratory reports so the sponsor, investigators, study coordinators, pharmacists, study subjects, and the CEC members will remain blinded to the dosing assignment.

The baseline value will be the latest value obtained prior to Day 1. Change from baseline for all continuous parameters will be calculated as the post-baseline value minus the baseline value. All continues variables will be summarized by number of subjects [n], mean, SD, Q1, median, Q3, minimum and maximum and categorical

1007728

variables will be summarized by frequency and percentage.

All scheduled and unscheduled results will be considered in tables that assess maximum grade or toxicity.

Observed values (in SI units) and change from baseline over time will be summarized by treatment group. Laboratory data will be classified as low, normal, or high relative to the parameter's reference range. Laboratory abnormalities for each treatment will also be summarized with shift tables for selected parameters.

All laboratory data will be listed. For hematology, chemistry, and serum lipids, columns will be included for normal ranges and individual abnormal laboratory values will be flagged and clinical significance will be indicated. A listing for the microscopic examination will be provided for subjects who have a positive result from the urinalysis dipstick evaluation.

Table 4 List of Laboratory Tests

Test Name (sample volume)		
Hematology (2 mL blood)		
 Mean corpuscular hemoglobin (MCH) Mean corpuscular hemoglobin concentration (MCHC) 	 Mean corpuscular volume (MCV) White blood cell (WBC) count with differential 	 Red blood cell (RBC) count Hematocrit (Hct) Hemoglobin (Hgb) Platelet count
Serum Chemistry and Electrolyte	es (3 mL serum)	
• Albumin (ALB)	• Calcium (Ca)	• Glucose
• ALT	• Magnesium	• Bicarbonate (HCO ₃)
• AST	• Phosphorus	• Chloride (Cl)
• Blood urea nitrogen (BUN)	• Potassium (K)	 Total bilirubin
• Creatinine	• Sodium (Na)	• Direct bilirubin
• Uric acid	• Total Protein	
Glycemic Control (2 mL plasma,	2 mL blood)	
• FPG	• HbA1c	
Serum Lipids		
 Total cholesterol (TC) High-density lipoprotein cholesterol (HDL-C) 	 Low-density lipoprotein cholesterol (LDL-C), calculated, or LDL-C, direct 	• Triglycerides (TG)

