Infectious Disease Testing (3 mL	serum)	
• Hepatitis B surface antigen (HBsAg)	• Hepatitis C virus (HCV)	
Urinalysis		
• Appearance	 Microscopic examination of sediment 	• pH
• Bilirubin	• Nitrite	• Protein
• Color	• Leukocyte esterase	• Specific gravity
• Glucose (blinded)	Occult blood	 Urobilinogen
• Ketones Renal Functional Test		
• UACR		
Urine Pregnancy Test		

1007728

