Table 14.3.1.1	Overall Summary of Treatment-Emergent Adverse Events (Safety
ומטוכ וא.ט.ו.ו	Analysis Set)

Number	Title
Table 14.3.1.2	Treatment-Emergent Adverse Events by System Organ Class and Preferred Term (Safety Analysis Set)
Table 14.3.1.3	Treatment-Emergent Adverse Events by System Organ Class, Preferred Term and Maximum Severity (Safety Analysis Set)
Table 14.3.1.4	Treatment-Emergent Adverse Events by System Organ Class, Preferred Term and Relationship to Study Drug (Safety Analysis Set)
Table 14.3.1.5	Most Common Treatment-Emergent Adverse Events by System Organ Class and Preferred Term (Safety Analysis Set)
Table 14.3.1.6	Treatment-Emergent Serious Adverse Events by System Organ Class and Preferred Term (Safety Analysis Set)
Table 14.3.1.7	Serious Treatment-Emergent Treatment Related Adverse Events by System Organ Class, Preferred Term and Relationship to Study Drug (Safety Analysis Set)
Table 14.3.1.8	Summary of Treatment Related Treatment-Emergent Adverse Events by System Organ Class and Preferred Term (Safety Analysis Set)
Table 14.3.1.9	Summary of Treatment Emergent Adverse Events Leading to Treatment Discontinuation by System Organ Class and Preferred Term (Safety Analysis Set)
Table 14.3.1.10	Summary of Treatment Emergent Adverse Events of Interest (Safety Analysis Set)
Table 14.3.1.11	Summary of Treatment Emergent Hypoglycemia Events (Safety Analysis Set)
Table 14.3.1.12	Summary of Major Adverse Cardiovascular Events (Safety Analysis Set)
Table 14.3.1.13	Summary of Revascularization and Amputations (Safety Analysis Set)
Table 14.3.2.1	List of Treatment Related TEAEs (Safety Analysis Set)
Table 14.3.2.2	List of Serious Adverse Events (Safety Analysis Set)
Table 14.3.2.3	List of Adverse Events Leading to Treatment Discontinuation (Safety Analysis Set)
Table 14.3.2.4	List of Adverse Events Leading to Death (Safety Analysis Set)
Table 14.3.4.1	Summary of Hematology: Results and Change from Baseline by Visit (Safety Analysis Set)
Table 14.3.4.2	Shift in Clinical Laboratory Values: Hematology (Safety Analysis Set)
Table 14.3.4.3	Summary of Serum Chemistry: Results and Change from Baseline by Visit (Safety Analysis Set)

Version 2.0

THR-1442-C-450

Number	Title
Table 14.3.4.4	Shift in Clinical Laboratory Values: Serum Chemistry (Safety Analysis Set)
Table 14.3.4.5	Summary of Urinalysis: Results and Change from Baseline by Visit - Continuous Variables (Safety Analysis Set)

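### The SAP 14 rule that halves results recorded with < or ≤ has no parameter exception, so censored urine specific gravity or pH would enter summaries at implausible values

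*SAP*

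**What the plan says.** SAP 14 (Programming Considerations) sets conventions for all outputs. Under its item on non-numeric values:

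- For results recorded with < or ≤, "the numeric portion of the result divided by 2 will be used". The worked example turns both <10 and ≤10 into 5.
- For results recorded with > or ≥, "the numeric portion of the result will be used", so >10 and ≥10 both become 10.
- The substitution is for summaries only. The recorded results "will appear in listings".

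Neither SAP 14 nor SAP 9.4 (Laboratory Evaluations) exempts any parameter.

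SAP Table 4 and Protocol Table 1 list pH and "Specific gravity" under urinalysis. SAP 9.4 says of laboratory data: "All continues variables will be summarized by number of subjects [n], mean, SD, Q1, median, Q3, minimum and maximum". The index in SAP 16 includes Table 14.3.4.5, a by-visit summary of continuous urinalysis variables with change from baseline. It does not name the variables.

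On the source of the data, Protocol 6.9.2.2 says "Urine samples will be transported to the central laboratory for urinalysis". No reporting limits are given for either test.

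**The concern.** Replacing <x by x/2 is a reasonable convention for a concentration whose true value lies somewhere between zero and x. It fails where the scale does not run down to zero in that way. Specific gravity is a density ratio to water and sits near 1, so half a limit near 1 describes no urine sample. pH is logarithmic, so halving it has no meaning as a midpoint.

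The rule is also asymmetric. A result of ≤x may equal x exactly, yet it is halved, while ≥x stays at x. That is visible on the page whatever the laboratory reports.

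At stake is the readability of one descriptive safety table. A program that follows the SAP literally would put impossible values into the mean, SD, minimum and change from baseline. Correcting them after the output is seen would mean departing from a stated convention.

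**Working it through.** **Reproducing the plan's own figure.** The rule applied to the SAP's example gives 10/2 = 5, as stated.

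**Applying the rule to the two tests.** The limits 1.005 and 5.0 are assumptions, since the documents give none.

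- Specific gravity ≤1.005: 1.005/2 = 0.5025.
- pH ≤5.0: 5.0/2 = 2.5.
- Change from an assumed baseline specific gravity of 1.020: 0.5025 - 1.020 = -0.5175. Using the limit itself gives 1.005 - 1.020 = -0.015.
- Change from an assumed baseline pH of 6.0: 2.5 - 6.0 = -3.5. Using the limit itself gives 5.0 - 6.0 = -1.0.

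**Effect on a visit summary.** Let a share f of results be at the limit L and enter as v, where v = L/2 under the SAP rule or v = L if the limit is kept. Let the other results have mean m and SD s. Then:

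- mean = f·v + (1 - f)·m
- variance = (1 - f)·s² + f·(1 - f)·(m - v)²
- shift in mean caused by halving = f·(L/2 - L) = -f·L/2

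Assumed inputs are m = 1.020 and s = 0.007 for specific gravity, and m = 6.0 and s = 0.6 for pH.

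Example for specific gravity at f = 1%:

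- Shift: -0.01 × 0.5025 = -0.005.
- Halved: variance = 0.99 × 0.007² + 0.0099 × 0.5175² = 0.0000485 + 0.0026513 = 0.0026998, so SD = 0.0520.
- Limit kept: variance = 0.0000485 + 0.0099 × 0.015² = 0.0000507, so SD = 0.0071.
- Ratio of SDs: 7.3.

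| Test | f | Mean (SD), halved | Mean (SD), limit kept | Shift | SD ratio |
|---|---|---|---|---|---|
| Specific gravity | 0 | 1.0200 (0.0070) | 1.0200 (0.0070) | 0 | 1.0 |
| | 1% | 1.0148 (0.0520) | 1.0198 (0.0071) | -0.0050 | 7.3 |
| | 2% | 1.0096 (0.0728) | 1.0197 (0.0072) | -0.0101 | 10.1 |
| | 5% | 0.9941 (0.1130) | 1.0192 (0.0076) | -0.0251 | 14.9 |
| | 20% | 0.9165 (0.2071) | 1.0170 (0.0087) | -0.1005 | 23.9 |
| pH | 0 | 6.00 (0.60) | 6.00 (0.60) | 0 | 1.0 |
| | 1% | 5.965 (0.691) | 5.990 (0.605) | -0.025 | 1.1 |
| | 5% | 5.825 (0.961) | 5.950 (0.624) | -0.125 | 1.5 |
| | 20% | 5.300 (1.499) | 5.800 (0.669) | -0.500 | 2.2 |

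For scale, one such record among the 70 subjects planned for placebo is 1/70 = 1.4%, between the 1% and 2% rows. Specific gravity is far more sensitive than pH because its spread is small relative to the size of the substitution error.

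**The case against.** The strongest objection is that nothing in the documents triggers the problem. They do not say that specific gravity or pH is ever reported with < or ≤. They give no reporting limits and refer to a Laboratory Manual that is not available here. Table 14.3.4.5 names no variables and its shell is not shown. Urinalysis protein, ketones or urobilinogen, or the albumin-to-creatinine ratio, might be its content instead, and x/2 could be suitable for some of these. All of this stands, and it is why the point is conditional.

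A second objection is that the error would be caught. A printed minimum specific gravity near 0.50 is plainly impossible. The sponsor reviews all tables (SAP 2.1), outputs go through quality control (SAP 15), and SAP 14 allows documented changes during programming. The quartiles would also hardly move at small shares. This limits the harm, but it does not make the rule right. It only means that the repair would come after the output was seen.

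A third objection is that x/2 is a common convention and the SAP states its treatment of ≤ explicitly. That is fair for <x on a zero-bounded concentration. It does not defend halving a ratio near 1 or a logarithmic scale.

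A reader might also infer a false difference between arms: the drug raises urinary glucose, so dilute samples might be rarer on bexagliflozin, which would mislead on volume-related safety. The documents do not support that. They give no rates of below-limit results by arm and do not say that the drug changes specific gravity. They assess diuretic effects and hypotensive episodes through adverse-event terms (SAP 9.3.3), not through specific gravity. No arm difference is claimed here.

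**Conclusion.** The point holds as a conditional defect in a stated rule. SAP 14 halves < and ≤ results in summaries without exception, and that is invalid for specific gravity and pH. If the laboratory reports either test in that form, and if they are in Table 14.3.4.5, the mean, SD, minimum and change from baseline would be distorted. Under the assumed limit and distribution for specific gravity, the mean shift is about -0.005 with a 7-fold SD at 1% of results, and about -0.025 with a 15-fold SD at 5%. The effect is zero if no such results occur.

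It would be too strong to conclude that the table is corrupted, or that recorded data are altered. The first depends on laboratory reporting that the documents do not describe, and the listings keep the recorded result. The affected output is descriptive. The primary analysis (HbA1c) and the key secondary analyses (systolic blood pressure and body weight) use other variables and are not touched. This is a minor point, worth making because the rule is wrong as written and very cheap to correct.

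**What to change.** Amend the non-numeric rule in SAP 14 as follows:

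- Use x/2 only for results recorded as <x on quantities bounded below by zero.
- For urine specific gravity, pH and any similar scale, use the reported limit x.
- For ≤x generally, use x, matching the existing treatment of ≥x.

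With this change the assumed examples enter as 1.005 and 5.0. The cost is about one sentence in the SAP and one line of code, with no new data. It should be made before unblinding, so that it stands as a convention and not as a correction to seen output. Checking with the central laboratory whether either test is ever reported with an inequality sign would show whether the change has any practical effect.
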